## **Screening Failures and Drop Outs patients**

For the purpose of this study, an “enrolled patient” is a patient who has signed the informed consent and meets all inclusion and exclusion criteria to participate in the study.

A “screening failure” is a patient who has signed the informed consent, but who does not meet all selection criteria and has not received any study medication as part of this protocol.

For patients not considered eligible after the screening period, the reason for not being eligible must be documented. No additional assessments are needed.

A “drop-out” is a patient who has received the study medication and withdrawn consent during the participation in the trial. A “drop-out” may also be a patient who has been “lost to follow-up” and is presumed to have withdrawn consent prior to the end of the trial procedures. However, in the case where a patient who has signed the informed consent and has received study medication as part of this protocol, but who is (later) found not to meet all selection criteria, this will be considered a “protocol violation”.

## **Discontinuation Criteria for Individual Patients**

The patient is free to withdraw from the study for any reason and at any time without giving reason for doing so and without penalty or prejudice. It is also possible that the Sponsor or Swissmedic request termination of the study if there are concerns about conduct or safety.

A patient may be withdrawn from the study if:

- A serious adverse event (SAE) occurs.
- The patient fails to comply with the evaluations or other requirements of the study.
- The patient starts treatment with one of the medications disallowed. The final decision to withdraw a patient who starts treatment with disallowed medication will be made by the Sponsor following consulting of the Investigator.

A patient must be withdrawn from the study if:

- The Investigator considers it, for safety reasons, to be in the best interest of the patient.
- The patient withdraws his/her consent.
- The patient is pregnant.

If withdrawal occurs for any reason, the Investigator must determine the primary reason for a patient's withdrawal from the study. The date and reason for discontinuation must be documented in the CRF.

For patients who are lost to follow-up (i.e., those patients whose status is unclear because they fail to appear for study visits without stating an intention to withdraw), the Investigator should show ‘due diligence’ by documenting in the source documents steps taken to contact the patient, e.g., dates of telephone calls, registered letters, etc.

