-------------------------	--

[figure not shown]
Immunogenicity assessments	
After complete decay of radioactivity, one out of two serum samples per time-point will be shipped to the central laboratory and analyzed by ELISA to determine the rhAnnexin V-128 concentration in serum (method detailed in the Laboratory Manual).
 
Assays for anti-rhAnnexin V-128 IgG and IgM antibodies will be performed in serum samples by ELISA. For this purpose 10mL blood samples will be collected at baseline, at Day 30 ± 3 days and at Day 56 ± 14 days. An additional sample is required 3 months after the first administration of the 99mTc-rhAnnexin V-128 (Day 90 ± 14 days) in case of positive anti-Annexin antibodies outcome in previous examinations. Serum will be prepared, divided into six aliquots and frozen (-80°C) until complete decay. Three out of six serum samples per time-point will be then shipped to the centralized laboratory, where the analysis for anti-rhAnnexin V-128 antibodies will be performed (methods detailed in the Laboratory Manual).
 
24 hours after each treatment injection (at Day 2 and Day 43), each patient will be interviewed over the phone (in face to face meeting at Day 2 for patients who will participate into the PK and dosimetric sub study) in order to inquire if they experienced signs or symptoms of allergic reactions (edema, rash). If this is the case, Adverse Event(s) should be reported and recorded in the Case Report Form.

Safety and tolerability	Adverse events will be collected in the Case Report Form (CRF).

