**Visit schedule – Table 1**

Study Procedures	Screening ( $\pm 4$ weeks)	Day 1	24 hours 	Day 30 $\pm 3$ days	Day 42 $\pm 2$ weeks	Day 56 $\pm 2$ weeks	Day 90 $\pm 2$ weeks
Written informed consent	X						
Inclusion/exclusion criteria	X						
Medical history	X						
Concomitant medications including RA and AS treatment	X	X	X	X	X	X	X
Disease assessment (BASDAI, BASFI, BASMI for AS for AS patients, DAS28 scales including Ultrasound assessments for RA patients)	X				X		X
Physical examination	X				X		X
Vital signs (BP and HR)	X	X	X	X	X	X	X
Lab analysis (haematology, biochemistry; urine)	X		X	X	X		X
Venous/urine sampling (PK and dosimetry) 		X 	X				
Immunogenicity by ELISA 	X			X		X	X
Urine SEC-HPLC analysis 		X	X				
Pregnancy test	X	X			X		
Standard 12-lead ECG	X	X	X	X	X		X
rh-Annexin V-128 administration 		X			X		
Bone scintigraphy 	X						
Whole Body scintigraphic imaging 		X	X		X		
Adverse Events	X	X	X	X	X	X	X

 Only for patients participating to the dosimetric and PK substudies.

 Venous blood samples of 10 ml volume each will be taken from the first 3 patients at nominal times of 0, 5, 10, 15, 30, 60 minutes and 2 hrs, 4hrs and 24 hrs post administration as described in Appendix 2 for radioactivity measurements, and PK. Depending upon the results in those 3 patients, timeframe of radioactivity measurements and PK will be confirmed or modified with a time-point at 3 hrs (instead of 2 hrs) and 6 hrs (instead of 4 hrs) as required for the following 7 enrolled patients in the sub-study. The whole blood and serum samples (bullet points 1 and 2) will be counted in an auto-gamma counting system at the CHUV/NUC laboratory.

 Anti-rhAnnexin V-128 IgG and IgM antibodies will be performed in serum samples by ELISA. For this purpose 10mL blood samples will be collected at baseline, Day 30 ( $\pm 3$  days), Day 56 ( $\pm 2$  weeks) and Day 90 ( $\pm 2$  weeks) post administration of test agent (sample at 90 days is required only in case of positive anti-annexin antibodies outcome in previous examinations). Serum will be prepared, divided into six aliquots and frozen (-80°C) until complete decay. Three out of six serum samples per time-point will be then shipped to the central laboratory.

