- Any adverse events post-injection will be followed until resolution. 24 hours after each treatment injection (at Day 2 and Day 43), each patient will be contacted by phone (except at Day 2 for patients participating in the PK and dosimetric sub-study who will be interviewed during in site visit) in order to inquire if they experienced signs or symptoms of allergic reactions (edema, rash).

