## **Adverse Events**

All original AEs terms will be coded using the Medical Dictionary for Regulatory Activities (MedDRA). System organ classes and preferred terms will be used in the analyses.

Type and incidence of AEs, as well as severity and relatedness to the study medication will be

tabulated. Special attention will be given to those patients who prematurely discontinue the study or the study medication due to an AE, or who experience a severe AE or an SAE.

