## Investigator Reporting Requirements

Throughout the study, the study staff will question the patient in a non-directive way as to the occurrence of AEs. The patient will also be instructed, when signing the informed consent, as from that moment, to contact the Investigator to report any study medication or non-study medication-related adverse or unusual event that occurs during participation to the study.

The study staff will record all these events in the patient's medical records and e-CRF, whether observed by the Investigator, the investigational staff, or spontaneously reported by the patient.

The Investigator will provide a complete description of the event in standard medical terminology, the date of onset and termination, severity, relationship to the study medication, action taken regarding the study medication, any treatment given, the outcome, and whether or not the event is considered an SAE. If known, the Investigator should report the underlying illness or disorder rather than the individual signs and symptoms.

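### Protocol section 4 ends study participation on a safety judgement or pregnancy without keeping the patient on the safety visits, so a dosed patient can leave with no required post-dose lab panel or antibody sample

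*Protocol*

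**What the plan says.** Protocol section 4, Discontinuation Criteria for Individual Patients, has an optional and a mandatory list. Both lead to withdrawal from the study.

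- The optional list covers an SAE, non-compliance and disallowed medication.
- The mandatory list opens "A patient must be withdrawn from the study if". It contains "The Investigator considers it, for safety reasons, to be in the best interest of the patient", withdrawn consent and pregnancy.
- The duty at that point is administrative: "The date and reason for discontinuation must be documented in the CRF". For patients lost to follow-up, contact attempts are documented as well.

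SAP 4.3 repeats this text. Table 1 and the SAP section 5 schema have no early-termination column.

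The 24-hour column of Table 1 carries the footnote "Only for patients participating to the dosimetric and PK substudies". The other patients get a telephone contact: "24 hours after each treatment injection (at Day 2 and Day 43), each patient will be contacted by phone". If an allergic sign is reported, "If this is the case, Adverse Event(s) should be reported and recorded in the Case Report Form". Neither document ties a lab test or antibody sample to that answer.

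Elsewhere, stopping the product is recognised as an event of its own. Protocol section 8 says "Special attention will be given to those patients who prematurely discontinue the study or the study medication due to an AE". Section 9 has the investigator record "action taken regarding the study medication". Section 8 of the SAE form in Appendix 5 has columns for interruption. SAP 7.8.2 tabulates events leading to permanent treatment discontinuation, and SAP Table 14.1.1 has a row for withdrawal from treatment.

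**The concern.** Treatment is two injections about six weeks apart, so stopping it can only mean not giving injection 2. That is no reason to stop observing the effects of injection 1. Yet the only action section 4 describes is leaving the study, and for a safety judgement or a pregnancy it is mandatory.

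Safety and tolerability is the primary objective. Abnormal laboratory tests are a primary safety endpoint in SAP 6.1, and antibodies are a separate endpoint in SAP 6.3. A patient withdrawn because of how injection 1 was tolerated is one whose post-dose labs and antibody status are of most interest. Clinical care of an adverse event may well produce routine blood tests. It is unlikely to produce the anti-rhAnnexin V-128 result, which is a study-specific ELISA.

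**Working it through.** **1. What is due after dosing, outside the sub-study** (Table 1; Protocol section 6; Appendix 3)

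- Lab panels: Days 30, 42 and 90, so 3.
- Antibody samples: Days 30 and 56, plus Day 90. The documents conflict on Day 90. The synopsis visit description and Appendix 3 give it to everyone. Table 1 footnote 3, Protocol section 6 and SAP 6.3 require it only after an earlier positive. The count is therefore 2 or 3.
- The earliest Day 30 visit is 30 − 3 = Day 27.

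**2. Is an exit draw provided for anywhere?** The blood volumes in Appendix 3 and Protocol section 8 reproduce from scheduled draws alone.

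- Outside the sub-study: 4 × 15 + 4 × 10 = 100 ml, as stated.
- In the sub-study: 5 × 15 + 80 + 10 + 4 × 10 = 205 ml, as stated.

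No volume is left for a withdrawal sample.

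**3. What each case loses**

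- Outside the sub-study, withdrawn after Day 1 and before the Day 30 visit: 0 of 3 post-dose lab panels and 0 of 2 (or 0 of 3) antibody samples are required.
- In the sub-study, same timing: the Day 2 labs exist, but no post-dose antibody sample is required.
- Any patient withdrawn at Day 42, for example on a positive pregnancy test before injection 2: the Day 56 antibody sample and the Day 90 labs are lost, as is the Day 90 antibody sample if due.

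**4. What is not lost**

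- Adverse events are followed until resolution (Protocol sections 6 and 9).
- SAEs are collected to 30 days after the last dose, and section 11 of the SAE form asks for laboratory values.
- Anyone eligible and dosed once is in the Safety Set (SAP 7.3).
- Baseline data and Day 1 vital signs and ECG exist for everyone.
- Under SAP 7.1.2, unscheduled tests enter listings, shift tables and maximum and minimum changes, but not by-visit summaries.

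**5. Illustrative scale.** The plan's recruitment figure reproduces: 20 / (1 − 0.10) = 22.2, rounded up to 23. Planned outside the sub-study: 23 − 10 = 13.

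Assume that 10% non-completion applies equally inside and outside the sub-study, and let f be the share of non-completers who leave before the Day 30 visit. The documents do not give f. The expected number is 13 × 0.10 × f, and the chance of at least one is 1 − (1 − 0.10f)^13.

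| f | Expected patients | Chance of at least one |
|---|---|---|
| 0 | 0 | 0% |
| 0.25 | 0.3 | 28% |
| 0.5 | 0.65 | 49% |
| 1 | 1.3 | 75% |

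Even at f = 1, the chance of no more than two is 0.254 + 0.367 + 0.245 = 0.866. These counts include patients who withdraw consent or are lost, so the recoverable number is smaller.

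**The case against.** The strongest reply is that silence is not prohibition. Several places separate stopping the product from leaving the study, and nothing in section 4 bars a patient from missing injection 2 and staying on the visits. For a non-serious reaction, the gap opens only if the investigator decides on withdrawal. After an SAE, withdrawal is optional, and a severe allergic reaction treated intensively without admission would usually count as serious and so go on the SAE form. Safety analysis is descriptive, so no planned analysis becomes wrong.

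Most of this stands, and it limits the point. A reader might infer that the protocol forbids stopping treatment while staying in follow-up; it does not. What remains is that the mandatory rule, followed as written, takes the patient out of the study, and no text says that scheduled assessments continue.

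A reader might also infer that such patients vanish from the safety analysis. They do not: they stay in the Safety Set and the adverse event tables, and they contribute baseline and Day 1 data. Only later by-visit results are missing.

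Finally, a reader might take 23 − 20 = 3 as the most patients who could be affected. The documents do not support that. Ten per cent is an expectation, every non-completer is to be replaced, and 23 is a planned number. SAP 4.2 reports that recruitment was stopped early, with 80% or more of the planned sample evaluable (at least 0.80 × 20 = 16).

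**Conclusion.** The point holds as a gap in follow-up rules that is cheap to close. It is not an error in any planned analysis. Withdrawal for safety or pregnancy is mandatory, carries no assessments, and is not separated from stopping the product. A patient outside the sub-study who is withdrawn between Day 1 and the Day 30 visit therefore has no required post-dose lab panel or antibody sample. Withdrawal at Day 42 costs the later ones.

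The number affected cannot be derived, because neither the timing of nor the reasons for non-completion are given. Zero to two is a judgement that rests on the planned 23 patients, the expected 10%, and equal non-completion inside and outside the sub-study. The actual number may be zero.

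**What to change.** In protocol section 4, state that a patient taken off for safety, an SAE or pregnancy is not given injection 2 but stays on the existing Day 30, 42, 56 and 90 labs, ECG, vital signs and antibody samples as scheduled, without injection or imaging, unless consent is withdrawn. This part restores the by-visit data.

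For patients who leave the study, request one final set of the existing safety tests and report it as unscheduled under SAP 7.1.2. This is of secondary value. It stays out of by-visit summaries, and an antibody sample taken well before Day 30, the first post-dose time the plan tests, may be uninformative.

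The cost is some extra attendance by patients who have stopped, one exit set for those who leave, and a protocol amendment with sponsor, Swissmedic and ethics committee approval where applicable. No new test is needed. Recruitment was to stop by the end of September 2017 and the SAP is dated 26/01/2018, so a change at that date would help few or none of this trial's patients. Its main use is in later protocols for this agent.

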## **Prohibition and Restrictions**

Previous Annexin V-based agents, such as 99mTc-BTAP-rhAnnexin V and 99mTc-HYNIC-rhAnnexin V, have been used in several clinical trials as a tool for both diagnosis and follow up of drug therapy in oncological, autoimmune, transplanted and cardiopathic patients. No significant effects on vital signs, coagulation parameters or measured haematology or chemistry values have been observed.

Existing Phase I study data in healthy volunteers, indicates that 99mTc-HYNIC-rhAnnexin V is a safe radiopharmaceutical [28].

The good safety profile of 99mTc-rhAnnexin V-128 has been confirmed by the extensive package of bioanalytical, immunological and other preclinical studies performed by the Sponsor which indicate adequate safety margin for use in man at the concentrations and doses foreseen in this study.

Furthermore, no adverse reactions were observed in a Phase I study in 12 healthy volunteers who have been administered 370 MBq of 99mTc-rhAnnexin V-128.

The most important required restriction for study patients is pregnancy.

Imaging is performed ambulatory. After imaging, patient may go back home or go back to work without particular precaution for him or his relatives.

Any concomitant medication deemed necessary for the welfare of the subject during the study may be given at the discretion of the Investigator. However, it is the responsibility of the Investigator to ensure that details regarding the medication are recorded in full in the case report form, including any changes that have occurred during the study.

## **5 STUDY MEDICATION AND TREATMENT**

### **Packaging and Labelling**

The full name of the Investigational New Drug is "Kit for the Preparation of Tc-99m Recombinant Human Annexin V-128 for Injection".

The kit will be prepared, packaged and released according to Sponsor Standard Operating Procedures (SOPs), Good Manufacturing Practice (GMP) guidelines, ICH Good Clinical Practice (GCP) guidelines, and applicable local laws/regulations.

The investigational product will be supplied by Sponsor as a sterile, single vial lyophilised kit for reconstitution with 99mTc solution eluted from a generator.

A single dose vial contains 0.4 mg of rhAnnexin V-128. The kit also contains stannous chloride (reducing agent), sodium α-D-Glucoheptonate dihydrate (transchelating agent), gentisic acid sodium salt hydrate (radiation stability enhancer), hydroxypropyl-β-cyclodextrin (solubilizer), sodium metabisulfite (antioxidant) and trehalose dihydrate (lyoprotectant and cake-forming agent). Lactic acid is also present as buffering agent. The kit composition details are reported in the table below.

Composition of the Kit for the preparation of 99mTc-rhAnnexin V-128 for injection

Component	Amount mg/ vial	Function	Reference to Standards
rhAnnexin V-128	0.400	Drug Substance	In-house
Sodium α-D-Glucoheptonate dihydrate	3	Transchelating agent	In-house
Gentisic acid sodium salt hydrate	0.020	Radiation Stability Enhancer	In-house
D(+)-Trehalose dihydrate	50	Lyoprotectant/Cake forming agent	Ph. Eur. 07/2010:2297
Sodium metabisulfite	0.020	Lyoprotectant	Ph. Eur. 01/2008:0849
Hydroxypropyl-β-Cyclodextrin	5	Solubilizing agent	Ph. Eur. 01/2009:1804

Stannous chloride dihydrate	0.010	Reducing agent	Ph. Eur. 01/2008:1266
Lactic acid	5.406	Buffering agent	Ph. Eur. 01/2008: 0458
Sodium hydroxide	1.320	pH regulation agent	Ph. Eur. 01/2008: 0677
Nitrogen	qs	Inert blanket	Ph. Eur. 01/2008:1247

## **Handling of Study Medication**

*99mTc-rhAnnexin V-128 must be administered at the investigational site.*

The study medication must be stored, handled and administered only by qualified/authorized personnel and must be prepared in accordance with pharmaceutical quality requirements, and radiation safety regulations.

Based on the stability tests performed (Appendix 1), the Annexin Kit can be stored upon receipt at 5°C ± 3°C at least up to 6 months..

A single dose vial containing 0.4 mg of lyophilized rhAnnexin V-128 will be reconstituted with 2 mL ± 0.2 mL containing 740 MBq ± 74 MBq (20 mCi ± 2 mCi) of 99mTc eluted from the generator. Stability studies have demonstrated radiochemical purity at 6 h from labelling greater than 90%, which is in line with current specifications of the Kit for the preparation of 99mTc-rhAnnexin V-128 for injection. The administration volume (corresponding to 250 MBq) is calculated according to the estimated time of injection, on the basis of the physical decay of the radionuclide (half-life = 6.02 h). For the purpose of this study, it is recommended to administer the reconstituted solution within 4 hours after completion of the labelling reaction.

## **IMP Packaging and Storage**

The site personnel will maintain shipping, dispensing, and collection logs. All investigational product will be stored and inventoried according to the protocol instructions and applicable state, regional and federal regulations and will be stored in a secure, locked location with limited authorized access at the investigational site.

## **Precautions and recommendation for use**

Technetium-99m eluate should be obtained from a commercially available Mo-99/Tc-99m generator, approved by regulatory authorities, that has been eluted within the past 24 hrs. The radiopharmacist will be directed to use the eluate within one hour of milking the generator.

Drug inventory and accountability records for the "Kits for preparation of Technetium 99mTc-rhAnnexin V-128 for injection" will be kept by the Investigator/the radiopharmacist, and must be documented throughout the study.

On ongoing basis the Investigator/radiopharmacist agrees to conduct a study medication supply inventory and to record the results of this inventory on the IMP Reconciliation Form. It must be possible to reconcile delivery records with those of used and unused medication. Any discrepancies must be accounted for. Appropriate forms of deliveries and returns must be signed by the responsible person.

Used/unused "Kits for preparation of Technetium 99mTc-rhAnnexin V-128 for injection" will be locally discarded after monitoring by the Clinical Research Associate.

Refer to Appendix 1 for detailed instruction on the Radiolabelled Imaging Product 99mTc-rhAnnexin V-

128, Cautionary notes, Analytical and Biological Controls, Stability and Shelf Life.

### **Study Medication Dose, Mode of Administration, Batch Number**

The "Kit for preparation of 99mTc-rhAnnexin V-128 for injection" consists of 1 patient dose.

The single dose vial (0.40 mg rh-Annexin V-128) will be reconstituted with 2 mL ± 0.2 mL containing 740 MBq ± 74 MBq (20 mCi ± 2 mCi) of 99mTc. The labelling reaction requires 90 minutes and the reconstituted radiolabelled product is stable for 6 h. For the purpose of this study, it is recommended to administer the reconstituted solution within 4 hours after completion of the labelling reaction,

Patients will receive 2 administrations of 99mTc-rhAnnexin V-128 , one on day 1 and one on day 42 (±14 days).

When investigational product is received at the site, the Investigator, Pharmacist or authorized designee shall check for accurate delivery and acknowledge receipt by signing and dating the documentation provided by the Sponsor and returning it to the Sponsor or designee. A copy of this documentation shall be retained for the Investigator file.

The dispensing of the investigational product shall be carefully recorded on an investigational product accountability form provided and an accurate accounting must be available for verification by the Clinical Research Associate at each monitoring visit.

Unused investigational product must not be discarded or used for any purpose other than the present study.

The Clinical Research Associate will periodically collect the Drug Accountability Forms and will check all investigational product (both unused and used) before making arrangements for authorizing their destruction at the investigational site.

